Study Protocol and Statistical Analysis Plan

Official Title of the study: Effects of erythropoietin on acute kidney injury in patients undergoing cardiac surgery

ID: CSA-AKI2016

NCT03007537

Document Type: Study Protocol with Statistical Analysis Plan

Document Date: August 4, 2020

Acute renal injury (AKI) often occurs after cardiac surgery, while the incidence of cardiac surgery associated acute kidney injury (CSA- AKI) increases significantly in patients undergoing cardiopulmonary bypass during operation. The incidence of CSAAKI published in the current study was 8.9~39.0 %. Need of renal replacement therapy (RRT) was 1%~5% after operation, while the total mortality rate was about 1.4%. Studies have shown that even minor postoperative AKI of elevated serum creatinine was significantly associated with higher mortality. Thus, the prevention of CSA-AKI is of great importance to improve the prognosis of patients. At present, the availability of effective drugs for CSA-AKI prevention drugs is still limited.

Erythropoietin (EPO) is a kind of substance secreted by renal cortical tubulointerstitial cells and liver which is commonly used in the treatment of renal anemia. Studies have shown that EPO can prevent AKI due to the effect of potential anti-apoptotic and antioxidant. Previous documents also proved that EPO could improve renal function AKI models in rats. The safety of preoperative use has been preliminarily confirmed by some studies, but the conclusion of the effectiveness of renal protection still remains on controversial. The 2012 guidelines of AKI from Kidney Disease Improving Global Outcome (KDIGO) recommended randomized controlled studies conducted for EPO prevention of AKI. This study aimed to explore whether clinical use EPO can reduce the risk CSA-AKI in patients and improve the prognosis.

1 Object and Methods

1.2 Research methodology

This study was a single-center randomized controlled clinical trial (RCT). For patients recruited in the study, preoperative information and some laboratory test results were collected. Patients were randomly assigned 1:1 to the EPO group and the control group using the predetermined random allocation table. The EPO group received 10000 IU of single hypodermic injection 24 hours before the operation, and the control group received equal volume of normal saline. At the same time, all subjects were followed up in hospital 7 days after the operation.

The test indicators included routine blood test, routine urine test and renal function test. Samples of blood and urine were collected at multiple time points before and after the surgery to detect early indicators of renal injury and inflammation. Including neutrophil Gelatinase associated lipocalin (NGAL), interleukin (IL-18), urinary kidney injury molecule-1 (KIM-1), C-reactive protein (CRP), IL-6, etc. Other clinical index such as occurrence of postoperative AKI, length of hospital stay, intensive care unit stay time, renal replacement therapy (require renal replacement therapy), death, acute physiology and chronic health evaluation (APACHE II) score, lung infections, etc. were collected.

The diagnosis of AKI after cardiac surgery was based on the 2012 KDIGO AKI Guidelines. This study followed the Declaration of Helsinki and was approved by the Ethics Committee of Nanjing First Hospital (KY20160721-02).

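### AKI is implied as the main outcome but never designated primary, so the plan does not limit which of its 12 named variables may carry the conclusion

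*Combined protocol and SAP*

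**What the plan says.** Several parts of the combined protocol and SAP point to AKI. The title is "Effects of erythropoietin on acute kidney injury in patients undergoing cardiac surgery" and the identifier is "ID: CSA-AKI2016". The rationale in the opening text says "Thus, the prevention of CSA-AKI is of great importance to improve the prognosis of patients". AKI is also the only outcome given a diagnostic standard, the 2012 KDIGO guideline (section 1.2).

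The aim has two parts: "This study aimed to explore whether clinical use EPO can reduce the risk CSA-AKI in patients and improve the prognosis". The second part is linked to no variable anywhere in the document.

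Section 1.2 sets out what is collected. Among the early markers of renal injury and inflammation it gives "Including neutrophil Gelatinase associated lipocalin (NGAL), interleukin (IL-18), urinary kidney injury molecule-1 (KIM-1), C-reactive protein (CRP), IL-6, etc". It then turns to "Other clinical index such as occurrence of postoperative AKI, length of hospital stay, intensive care unit stay time", followed by renal replacement therapy (RRT), death, APACHE II score and lung infection. Both lists close with an et cetera.

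Section 1.3 assigns tests by type of data: t-test for normally distributed continuous data, repeated-measures ANOVA for multiple time points, and Pearson chi-square for categories. It states no significance level, sidedness, order of testing or multiplicity adjustment. No section labels any outcome primary or secondary.

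**The concern.** A plan should fix, before results are known, which result decides the question. Here a reader can guess AKI, but nothing binds a report to that guess. If AKI turned out negative, the text would still allow a nominally positive biomarker to be presented as renal protection, or a shorter stay as better prognosis. For the prognosis part of the aim there is not even an implied choice, so a reader cannot tell which result was meant to decide it.

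What is at stake is the meaning of a positive conclusion. If one variable was fixed in advance, the usual error rate applies. If any of a dozen will do, it does not.

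**Working it through.** The plan states no alpha, power or sample size, so there is no figure of its own to reproduce. The steps below count the variables and show how much the missing designation could matter.

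**1. Count (section 1.2).** Biomarkers: NGAL, IL-18, KIM-1, CRP, IL-6 = 5. Clinical indices: AKI, hospital stay, ICU stay, RRT, death, APACHE II, lung infection = 7. Total 5 + 7 = 12 named variables. Both lists are open, and routine laboratory tests and multiple sampling times come on top. On the other hand, a variable that is collected need not be tested.

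**2. Assumptions, none of them in the documents.** Each of the 12 is tested once at two-sided 5%; there is no true effect on any; test statistics share a common correlation ρ; arm sizes, where needed, are 50, 100 or 150.

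**3. AKI alone, chosen in advance.** The opening text gives "The incidence of CSAAKI published in the current study was 8.9~39.0" percent. Summing the binomial probabilities of every pair of event counts for which the Pearson chi-square exceeds 3.84, at incidences of 8.9% and 39.0% and the assumed arm sizes, gives a true error rate of 0.0485 to 0.0519. A single AKI test keeps its nominal 5%.

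**4. Any of the 12, independent.** 1 − 0.95^12 = 1 − 0.540 = 0.460.

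**5. Any of the 12, correlated.** With c = 1.96, φ and Φ the standard normal density and distribution function, and the statistics sharing one common factor u,

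P = 1 − ∫ φ(u) [Φ((c − √ρ·u)/√(1−ρ)) − Φ((−c − √ρ·u)/√(1−ρ))]^12 du.

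| ρ | Chance of at least one false positive, 12 variables |
|---|---|
| 0 | 0.460 |
| 0.3 | 0.397 |
| 0.5 | 0.319 |
| 0.7 | 0.232 |
| 0.9 | 0.135 |

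**6. Rare events.** The opening text also gives "Need of renal replacement therapy (RRT) was 1%~5% after operation, while the total mortality rate was about 1.4" percent. Chi-square tests on such rare events can be very conservative. At 50 per arm the exact size is 0.0052 for death at 1.4% and 0.0019 for RRT at 1%, so the independent figure becomes 1 − 0.95^10 × 0.9948 × 0.9981 = 0.406. At 150 per arm with RRT at 5% the sizes are 0.0416 and 0.0484, giving 1 − 0.95^10 × 0.9584 × 0.9516 = 0.454. The 46% therefore becomes 41% to 45%.

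**7. Prognosis, if it meant all six clinical indices other than AKI.** Independent: 1 − 0.95^6 = 0.265. The formula in step 5 with exponent 6 gives 0.164 at ρ = 0.7 and 0.108 at ρ = 0.9.

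No figure is given for false positives favouring EPO in the 12-variable set. The biomarkers are sampled repeatedly, so section 1.3 assigns them repeated-measures ANOVA. A group-by-time F-test over more than two time points has no single direction.

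**The case against.** The strongest reply is that AKI is obviously the main outcome. The title, ID, first part of the aim and diagnostic standard all say so, no rival is suggested, and section 1.2 sets the biomarkers apart as early indicators. This largely stands. The gap concerning AKI is a missing label rather than real doubt about intent. It does not cover the prognosis aim, and an implied choice does not stop another variable from carrying the conclusion.

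A second reply is that section 1.2 says the variables are collected, not that each will be tested for a claim. APACHE II has no stated time point and may be a severity descriptor. This also stands. Twelve counts listed variables, and the number of tests is unknown in both directions. Dropping APACHE II changes little (1 − 0.95^11 = 0.43 if independent), but a reader might take 46% as this trial's error rate, and the documents do not support that. It requires 12 independent tests and a willingness to claim success on any one of them. The plan states no such rule, and independence is implausible for overlapping renal measures such as AKI, RRT, NGAL and KIM-1.

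A third reply is that the aim is worded as exploratory. That is correct: the plan does not promise family-wise control and is not faulted for lacking it. An exploratory study can still say which result its conclusion rests on.

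Finally, a reader might infer from the August 2020 document date, against recruitment from July 2016 to May 2017 (section 1.1), that AKI was picked after the data were seen. The date alone does not show this. The document is silent on when AKI was chosen, and an earlier dated record may exist elsewhere.

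**Conclusion.** The point holds in a limited form. AKI is implied but not designated primary, no rule restricts which of the 12 named variables may carry the conclusion, and the prognosis aim is attached to none of them.

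It would be too strong to say that the AKI comparison itself is inflated. Chosen in advance, it keeps about 5% (0.0485 to 0.0519 at the assumed arm sizes). The exposure is a claim resting on whichever variable is positive, illustrated by about 13% to 46% in either direction. That range rests on an assumed alpha of two-sided 5%, one test per variable, no true effects, and correlations from 0.9 down to 0. It shows the scale of the problem and is not a property of this plan.

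Severity is should-fix rather than must-fix, because the AKI test is unaffected if AKI was chosen beforehand. Adding a label now cannot supply that condition, so the timing of the choice has to be disclosed.

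**What to change.** 1. State first when AKI was chosen as the main outcome, citing any earlier dated record. If there is none, say that the timing is undocumented. If AKI was chosen after outcome data were seen, label the analysis post hoc.
2. Name AKI by KDIGO 2012 criteria, within the existing 7-day in-hospital follow-up, as the single primary endpoint at two-sided 5%, and rest the efficacy conclusion on it alone.
3. Label every other clinical index and biomarker secondary or exploratory, and state that none of them can carry the conclusion.
4. Have the investigators state which of the listed outcomes represent prognosis. That definition is theirs to give.

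The cost is wording and disclosure only; no new data are needed. The downside is that a positive biomarker or length-of-stay result could no longer support an efficacy claim alone. Undocumented timing would weaken the AKI result, though not void it.

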1.3 Statistical methods

SPSS (V22.0, SPSS, Inc., Chicago, IL, USA) and Graphpad Prism 8.0 software were used for data analysis. Continuous data subject to normal distribution were expressed as mean \pm standard deviation, and the independent sample T-test was used to compare the difference of the mean between the two groups. Repeated measurement design ANOVA was used to compare the differences between different groups at multiple time points. The categorical variables were presented as number (%) and compared by Pearson chi-square test.
